## **France**

### Section 5.4.1 Discontinuation of Individual Subjects

Subjects can request to be discontinued from participating in the study at any time for any reason including but not limited to disease progression or lack of response to treatment. The Investigator may discontinue any subject's participation for any reason, including an AE, safety concerns, lack of efficacy, or failure to comply with the protocol. See Section 6.1.7 for toxicity management criteria.

Subjects will have study drug discontinued immediately if any of the following occur:

- Clinically significant abnormal laboratory results or AEs, which rule out continuation of the study drug, as determined by the Investigator or the AbbVie Therapeutic Area Medical Director.
- Serious infections (e.g., sepsis) which cannot be adequately controlled within 2 weeks by anti-infective treatment or would put the subject at risk for continued participation in the trial as determined by the Investigator.
- The Investigator believes it is in the best interest of the subject.

- The subject requests withdrawal from the study.
- Inclusion or exclusion criteria violation was noted after the subject started study drug, when continuation of the study drug would place the subject at risk as determined by the AbbVie Therapeutic Area Medical Director.
- Introduction of prohibited medications or dosages when continuation of the study drug would place the subject at risk, as determined by the AbbVie Therapeutic Area Medical Director.
- Subject is non-compliant with TB prophylaxis (if applicable) or develops active TB at any time during the study.
- The subject becomes pregnant while on study drug.
- Malignancy.
- Subject is significantly non-compliant with study procedures which would put the subject at risk for continued participation in the trial as determined by the Investigator or the AbbVie Therapeutic Area Medical Director.
- Subject develops a gastrointestinal perforation.
- Starting at Week 24 and thereafter, subject fails to show at least 20% improvement in both TJC and SJC compared to baseline at 2 consecutive visits, despite optimization of background RA therapies.

In order to minimize missing data for efficacy and safety assessments, subjects who prematurely discontinue study drug treatment should complete a Premature Discontinuation visit (PD visit) as soon as possible, preferably within 2 weeks. Afterwards, subjects should continue to be followed for all regularly scheduled visits, unless they have decided to discontinue the study participation entirely (withdrawal informed consent). Subjects should be advised on the continued scientific importance of their data even if they discontinue treatment with study drug early.

If a subject prematurely discontinues study drug treatment and study participation (withdrawal of informed consent), the procedures outlined for the Premature Discontinuation visit (PD visit) should be completed as soon as possible, preferably within 2 weeks of study drug discontinuation. In addition, if subject is willing, a 30-day follow-up phone call (or visit) after the last dose of study drug may be completed to

ensure all treatment emergent AEs/SAEs have been resolved or the occurrence of any new AEs/SAEs. Subjects who discontinue the study prematurely after randomization will not be replaced.

All attempts must be made to determine the date of the last study drug dose and the primary reason for discontinuation of study drug or study participation. The information will be recorded on the appropriate eCRF page. However, these procedures should not interfere with the initiation of any new treatments or therapeutic modalities that the Investigator feels are necessary to treat the subject's condition. Following discontinuation of study drug, the subject will be treated in accordance with the Investigator's best clinical judgment irrespective of whether the subject decides to continue participation in the study.

#### Section 6.1.7 Toxicity Management

The toxicity management of the AEs including AEs of special interest consists of safety monitoring (review of AEs on an ongoing basis, and periodical/ad hoc review of safety issues by a safety data monitoring committee), interruption of study drug dosing with appropriate clinical management if applicable, and discontinuation of the subjects from study drug. The management of specific AEs and laboratory parameters is described below.

For subjects who discontinued study drug but continued study participation and are on standard of care therapies, these toxicity management requirements do not apply (including alerts from the central lab) and any intolerability to standard of care therapies should be managed by the prescribing physician.

**Serious Infections:** Subjects should be closely monitored for the development of signs and symptoms of infection during and after treatment with study drug. Study drug should be interrupted if a subject develops a serious infection or an opportunistic infection. A subject who develops a new infection during treatment with study drug should undergo prompt diagnostic testing appropriate for an immunocompromised subject. As appropriate, antimicrobial therapy should be initiated, and the subject should be closely

monitored. Re-challenge with study drug may occur once the infection has been successfully treated. Subjects who develop active TB must be discontinued from study drug.

**Herpes zoster:** If a subject develops herpes zoster, consider temporarily interrupting study drug until the episode resolves.

**Gastrointestinal Perforation:** If a diagnosis of gastrointestinal perforation is confirmed (other than appendicitis or penetrating injury), the subject must be permanently discontinued from study drug.

**Cardiovascular Events (MACE):** Subjects presenting with potential cardiovascular events should be carefully monitored. These events will be reviewed and adjudicated by an independent Cardiovascular Adjudication Committee in a blinded manner.

**Thrombosis Events:** Subjects who develop symptoms of thrombosis should be promptly evaluated and treated appropriately. If the diagnosis of deep vein thrombosis, pulmonary embolus or non-cardiac, non-neurologic arterial thrombosis is confirmed, the subject should be discontinued from study drug.

**Malignancy:** Subjects who develop malignancy must be discontinued from study drug. Information including histopathological results should be queried for the confirmation of the diagnosis. Periodic skin examination is recommended for subjects who are at increased risk for skin cancer.

**Management of Select Laboratory Abnormalities:** For any given laboratory abnormality, the Investigator should assess the subject, apply the standard of care for medical evaluation and treatment following any local guidelines. Specific toxicity management guidelines for abnormal laboratory values are described in [Table 5](#) and may require an appropriate supplemental eCRF to be completed. All abnormal laboratory tests that are considered clinically significant by the Investigator will be followed to a satisfactory resolution. If a repeat test is required per [Table 5](#), the repeat testing must occur as soon as possible.

**Table 5. Specific Toxicity Management Guidelines for Abnormal Laboratory Values (For France)**

Laboratory Parameter	Toxicity Management Guideline
Hemoglobin	
 
• If hemoglobin < 8 g/dL interrupt study drug dosing and confirm by repeat testing with a new sample.
 
• If hemoglobin decreases <math>\geq 3.0</math> g/dL from baseline without an alternative etiology, interrupt study drug dosing and confirm by repeat testing with new sample.
 
• If hemoglobin decreases <math>\geq 3.0</math> g/dL from baseline and an alternative etiology is known, the subject may remain on study drug at the investigator's discretion.
 
• If confirmed, continue to withhold study drug until hemoglobin value returns to normal reference range or its baseline value.
 

Absolute neutrophil count (ANC)	
 
• If confirmed < 1000 cells/<math>\mu</math>L by repeat testing with new sample, interrupt study drug dosing until ANC value returns to normal reference range or its baseline value.
 
• Discontinue study drug if confirmed < 500 cells/<math>\mu</math>L by repeat testing with new sample.
 

Absolute lymphocyte counts (ALC)	
 
• If confirmed < 500 cells/<math>\mu</math>L by repeat testing with new sample, interrupt study drug dosing until ALC returns to normal reference range or its baseline value.
 

Total white blood cell count	
 
• If confirmed < 2000 cells/<math>\mu</math>L by repeat testing with new sample, interrupt study drug dosing until white blood cell count returns to normal reference range or its baseline value.
 

Platelet count	
 
• If confirmed < 50,000 cells/<math>\mu</math>L by repeat testing with new sample, interrupt study drug dosing until platelet count returns to normal reference range or its baseline value.
 

**Table 5. Specific Toxicity Management Guidelines for Abnormal Laboratory Values (For France) (Continued)**

Laboratory Parameter	Toxicity Management Guideline
AST or ALT	
 
• Interrupt study drug immediately if confirmed ALT or AST > 3 × ULN by repeat testing with new sample and either a total bilirubin > 2 × ULN or an international normalized ratio (INR) > 1.5.               
 
○ A separate blood sample for INR testing will be needed to measure INR at the time of repeat testing for ALT or AST. A repeat test of INR is not needed for determination if above toxicity management criteria are met.
 
 
 
• Interrupt study drug immediately if confirmed ALT or AST > 3 × ULN by repeat testing with new sample along with appearance of fatigue, nausea, vomiting, right upper quadrant pain or tenderness, fever, rash, and/or eosinophilia (> 5%).
 
• Interrupt study drug immediately if confirmed ALT or AST > 8 × ULN by repeat testing with new sample.
 
• Interrupt study drug immediately if confirmed ALT or AST > 5 × ULN by repeat testing with new sample for more than 2 weeks.
 
 
Subjects who meet any of the above criteria should be evaluated for an alternative etiology of the ALT or AST elevation and managed as medically appropriate. If applicable, the alternative etiology should be documented in the eCRF. If ALT or AST values return to the normal reference range or its Baseline value, study drug may be restarted. If restarting study drug, documentation should include reason that rechallenge is expected to be safe. If after clinically appropriate evaluation, no alternative etiology for ALT or AST elevation is found or the ALT or AST elevation has not resolved or is not trending down toward normal, the subject should be discontinued from study drug.
 
 
• For subjects with HBc Ab+ (irrespective of HBs Ab status) and negative HBV DNA at screening who develop the following should have HBV DNA by PCR testing performed within one week:               
 
○ ALT > 5 × ULN OR
 
○ ALT or AST > 3 × ULN if an alternative cause is not readily identified.
 
 
 
• A positive result for HBV DNA PCR testing in these subjects will require immediate interruption of study drug and a hepatologist consultation should occur within 1 week for recommendation regarding subsequent treatment
 
 
For any confirmed ALT or AST elevations > 3 ULN, complete supplemental hepatic eCRF.

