**Period 2 (Long-Term Extension Period [236 Weeks])**

Period 2 will begin at the Week 24 Visit after all assessments have been completed. During Period 2, subjects will have a study visit at Weeks 36, 48, every 12 weeks through Week 240, and Week 260/PD. A  $\pm 7$  day window is permitted around scheduled study visits.

Starting at Week 24, at least 20% improvement in BOTH TJC AND SJC is required to remain on study drug. Anyone who does not fulfill this criterion at 2 consecutive visits (starting at Week 24) despite optimization of background RA therapies (see Section 5.2.3.1) must be discontinued from study drug.

Starting with Amendment 4, all subjects will receive open-label upadacitinib 15 mg QD, including those currently on upadacitinib 30 mg QD.

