## **5.4 Removal of Subjects from Therapy or Assessment**

### **5.4.1 Discontinuation of Individual Subjects**

Subjects can request to be discontinued from participating in the study at any time for any reason including but not limited to disease progression or lack of response to treatment. The Investigator may discontinue any subject's participation for any reason, including an AE, safety concerns, lack of efficacy, or failure to comply with the protocol. See Section 6.1.7 for toxicity management criteria.

Subjects will have study drug discontinued immediately if any of the following occur:

- Clinically significant abnormal laboratory results or AEs, which rule out safe continuation of the study drug, as determined by the Investigator or the AbbVie Therapeutic Area Medical Director.
- Serious infections (e.g., sepsis) which cannot be adequately controlled within 2 weeks by anti-infective treatment or would put the subject at risk for continued participation in the trial as determined by the Investigator.
- The Investigator believes it is in the best interest of the subject.
- The subject requests withdrawal from the study.
- Inclusion or exclusion criteria violation was noted after the subject started study drug, when continuation of the study drug would place the subject at risk as determined by the AbbVie Therapeutic Area Medical Director.
- Introduction of prohibited medications or dosages when continuation of the study drug would place the subject at risk, as determined by the AbbVie Therapeutic Area Medical Director.
- Subject is non-compliant with TB prophylaxis (if applicable) or develops active TB at any time during the study.
- The subject becomes pregnant while on study drug.
- Malignancy, except for localized NMSC or carcinoma in-situ of the cervix.
- Subject is significantly non-compliant with study procedures which would put the subject at risk for continued participation in the trial as determined by the Investigator or the AbbVie Therapeutic Area Medical Director.

- Subject develops a gastrointestinal perforation (other than due to appendicitis or mechanical injury).
- Starting at Week 24 and thereafter, subject fails to show at least 20% improvement in both TJC and SJC compared to baseline at 2 consecutive visits, despite optimization of background RA therapies.
- Confirmed diagnosis of deep vein thrombosis, pulmonary embolus or non-cardiac, non-neurologic arterial thrombosis.

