**Thrombosis Events:** Subjects who develop symptoms of thrombosis should be promptly evaluated and treated appropriately. If the diagnosis of deep vein thrombosis, pulmonary embolus or non-cardiac, non-neurologic arterial thrombosis is confirmed, the subject must be discontinued from study drug.

**Malignancy:** Subjects who develop malignancy other than NMSC or carcinoma in situ of the cervix must be discontinued from study drug. Information including histopathological results should be queried for the confirmation of the diagnosis. Periodic skin examination is recommended for subjects who are at increased risk for skin cancer.

**ECG Abnormality:** Subjects must be discontinued from study drug for an ECG change considered clinically significant and with reasonable possibility of relationship to study drug OR a confirmed absolute QTcF value > 500 msec.

**Management of Select Laboratory Abnormalities:** For any given laboratory abnormality, the Investigator should assess the subject, apply the standard of care for medical evaluation and treatment following any local guidelines. Specific toxicity management guidelines for abnormal laboratory values are described in [Table 4](#), and may require an appropriate supplemental eCRF to be completed. All abnormal laboratory tests that are considered clinically significant by the Investigator will be followed to a satisfactory resolution. If a repeat test is required per [Table 4](#), the repeat testing must occur as soon as possible.

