AST or ALT	
 
• Interrupt study drug immediately if confirmed ALT or AST <math>> 3 \times</math> ULN by repeat testing with new sample and either a total bilirubin <math>> 2 \times</math> ULN or an international normalized ratio <math>> 1.5</math>.               
 
○ A separate blood sample for INR testing will be needed to measure INR at the time of repeat testing for ALT or AST. A repeat test of INR is not needed for determination if above toxicity management criteria are met.
 
 
 
• Interrupt study drug immediately if confirmed ALT or AST <math>> 3 \times</math> ULN by repeat testing with new sample along with appearance of fatigue, nausea, vomiting, right upper quadrant pain or tenderness, fever, rash, and/or eosinophilia (<math>> 5\%</math>).
 
• Interrupt study drug immediately if confirmed ALT or AST <math>> 5 \times</math> ULN by repeat testing with new sample for more than 2 weeks.
 
• If ALT or AST <math>> 8 \times</math> ULN, interrupt study drug immediately, confirm by repeat testing with a new sample and contact the TA MD.
 
 
Subjects who meet any of the above criteria should be evaluated for an alternative etiology of the ALT or AST elevation and managed as medically appropriate. If applicable, the alternative etiology should be documented in the eCRF. If ALT or AST values return to the normal reference range or its Baseline value, study drug may be restarted. If restarting study drug, documentation should include reason that rechallenge is expected to be safe. If after clinically appropriate evaluation, no alternative etiology for ALT or AST elevation is found or the ALT or AST elevation has not resolved or is not trending down toward normal, the subject should be discontinued from study drug. For any confirmed ALT or AST elevations <math>> 3</math> ULN, complete supplemental hepatic eCRF.
 
 
• Subjects with HBc Ab+ (irrespective of HBs Ab status) and negative HBV DNA at screening who develop the following should have HBV DNA by PCR testing performed within 1 week:               
 
○ ALT <math>> 5 \times</math> ULN OR
 
○ ALT or AST <math>> 3 \times</math> ULN if an alternative cause is not readily identified.
 
 
 
 
A positive result for HBV DNA PCR testing in these subjects will require immediate interruption of study drug and a hepatologist consultation should occur within 1 week for recommendation regarding subsequent treatment.

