- If the subject must undergo emergency surgery, the study drug should be interrupted at the time of surgery. Allow reintroduction of study drug once the physician has examined the surgical site and determined that it has healed and there is no sign of infection.

Additional local requirements may apply. Refer to [Appendix C](#) for local requirements for France.

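### The France text in Appendix C was not brought into line with the current safety rules and does not say whether it adds to them or replaces them

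*Protocol*

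**What the plan says.** Protocol Sections 5.4.1 and 6.1.7 each end by referring French sites to Appendix C with the sentence "Additional local requirements may apply". Under France, Appendix C reprints most of both sections and then a complete laboratory table, Table 5, labelled as the French one. The French Section 6.1.7 sends the reader to Table 5, not to Table 4. No sentence says which text governs where they differ.

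On ALT or AST above 8 x ULN, Table 4 in the main text says to "interrupt study drug immediately, confirm by repeat testing with a new sample and contact the TA MD". Table 5 calls for interruption only when the value is confirmed above "8 × ULN by repeat testing with new sample", and mentions no contact with the TA MD. The French text does require promptness: "the repeat testing must occur as soon as possible".

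Main Section 6.1.7 also tells sites to interrupt drug for confirmed COVID-19. It requires discontinuation for a confirmed QTcF above 500 msec, or for a clinically significant ECG change with a reasonable possibility of relationship to drug. The French Section 6.1.7 contains neither paragraph.

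On thrombosis, main Section 5.4.1 lists "Confirmed diagnosis of deep vein thrombosis, pulmonary embolus or non-cardiac, non-neurologic arterial thrombosis" as a reason to stop at once. The French list has no such bullet, though the French Section 6.1.7 still directs that "the subject should be discontinued from study drug".

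**The concern.** Two sets of safety instructions stand side by side for French sites, and the protocol does not rank them. A site that works from the French reprint, because it looks complete and carries its own table, would wait for a repeat result before interrupting drug at ALT or AST above 8 x ULN. It would have no instruction specific to non-serious COVID-19 and no QTcF stopping threshold. The subjects concerned are those still on drug in the long-term extension. What is at stake is the safety conduct of the extension. Sample size, power, error control and the Week 12 results do not depend on it.

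**Working it through.** **How complete the reprint is.** This bears on whether a site could take it for a self-contained replacement.

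| Block | Main text | France |
|---|---|---|
| Stopping bullets, Section 5.4.1 | 13 | 12 (thrombosis absent) |
| Toxicity paragraphs, Section 6.1.7 | 9 | 7 (COVID-19 and ECG absent) |
| Laboratory rows, Table 4 or Table 5 | 8 | 8 |

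**Rule by rule.**

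| Point | Main text | France |
|---|---|---|
| ALT/AST > 8 x ULN | Interrupt at first value, confirm, contact TA MD | Interrupt only after confirmation; no TA MD contact |
| Confirmed COVID-19 | Interrupt | No specific rule |
| QTcF > 500 msec, or clinically significant drug-related ECG change | Discontinue | No specific rule |
| Confirmed thrombosis | Bullet in 5.4.1; *must* in 6.1.7 | No bullet in 5.4.1; *should* in 6.1.7 |

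That gives one weaker rule, two missing specific rules and one lesser mismatch. Section 1.1 lists the COVID-19 guidance and the TA MD contact at 8 x ULN among this amendment's changes to Section 6.1.7. This suggests that the main section was revised and the French copy was not.

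**Effect under each reading.**

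- *Addition.* The main rules bind in France. A site that interrupts at the first value above 8 x ULN has already interrupted by the time the value is confirmed, so following Table 4 also satisfies Table 5. No rule is lost.
- *Replacement.* The site follows the confirm-first rule and has no specific COVID-19 or ECG rule. Partial cover remains. The French Section 5.4.1 stops drug for clinically significant laboratory results or adverse events that rule out continuation, and when the investigator judges it best for the subject. The French Section 6.1.7 interrupts drug for serious or opportunistic infection. Section 6.1.4 is not reprinted, so COVID-19 event capture is unaffected.

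**Visits still open to the two rules that rest on scheduled tests.** Inputs: all subjects had reached the end of Period 1 (Week 24) as of September 2018 (Section 5.5.5.2); the synopsis is dated 08 December 2020; Appendix F schedules chemistry every 12 weeks and ECG every 48 weeks from Week 48 through Week 240.

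1. 30 September 2018 to 08 December 2020 is 800 days; 800 / 7 = 114.3 weeks.
2. The latest subject on schedule was then at about Week 24 + 114 = 138.
3. Chemistry visits left on drug, Weeks 144 to 240: (240 - 144)/12 + 1 = 9.
4. ECG visits left on drug, Weeks 144, 192 and 240: (240 - 144)/48 + 1 = 3.

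Week 260 is left out because no drug is dispensed at the final visit. These are upper limits. SAP Appendix B says Period 1 reporting was completed in 2017. Counting from 31 December 2017 gives 1,073 days, or 153.3 weeks, so about Week 177. That leaves 6 chemistry visits (Weeks 180 to 240) and 2 ECG visits (Weeks 192 and 240).

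**The case against.** The strongest counter-argument is the word *additional* in the pointer. Nothing in the protocol says the French text replaces Section 5.4.1 or 6.1.7, and on the addition reading no rule is lost. This stands, and it makes the harm conditional. It does not remove the ambiguity: the pointer says only that requirements may apply, while the appendix supplies a near-complete reprint that cites its own table. The other country texts do not settle the matter. Canada's male contraception period is 30 days against 90 in main criterion 11, but main Section 5.2.4 sets no male requirement at all, so that mismatch shows a separate drafting fault.

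Second, confirming before interrupting is common in this protocol. Main Table 4 does so for ALT or AST above 3 x ULN with raised bilirubin or INR, and for neutrophils, lymphocytes, white cells and platelets. With a prompt repeat required, the French delay is the time to one repeat test, for which the documents give no number of days. This also stands and makes the point modest. At 8 x ULN, however, the main text chose to interrupt first.

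Third, the French differences might be deliberate local requirements. The ones that look deliberate are stricter: no exceptions for malignancy, and any perforation in the French Section 5.4.1. The differences at issue are looser or missing, and no rationale is given. The French text also keeps Period 1 lines on methotrexate/placebo capsules and a 14-week period, which do not belong to this trial, and its Section 6.1.7 excepts some perforations that its Section 5.4.1 does not. That pattern points to unreconciled text.

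A reader might infer that thrombosis is no longer a stopping event in France. The documents do not support that, because the French Section 6.1.7 directs discontinuation. Nor does *should* in place of *must* carry much weight: for the 20% joint-count criterion, Section 5.1 says "must be discontinued from study drug" while a note to Appendix D uses *should*.

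**Conclusion.** The concern holds as an inconsistency between local and main text. The French text is out of step with the current main rules, weaker on ALT or AST above 8 x ULN and silent on COVID-19 interruption and the ECG stop, and the protocol does not state which text governs. The missing thrombosis bullet is a lesser point.

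Two stronger readings are tempting. A reader might infer that French subjects have lost these protections. The documents do not show that: the loss arises only if the reprint is read as a replacement, and partial cover remains even then. A reader might also count the whole Period 2 schedule, 18 chemistry visits (Week 36, plus 17 from Week 48 to Week 240) and 5 ECG visits. Most of those were past by the protocol date; at most 9 and 3 remained per subject.

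Those limits assume a subject who stays on schedule and on drug to Week 240, and take 30 September 2018 as the latest date for reaching Week 24. French enrolment is not given, so the number of subjects concerned is unknown. This is a minor to moderate safety-conduct correction with no bearing on any efficacy analysis or Period 1 result.

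**What to change.** Open the France section with a precedence sentence: *This text adds to the main protocol; where the two differ, the stricter safety rule applies.* This alone settles the listed conflicts and keeps the stricter French malignancy and perforation bullets. Then:

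- change the Table 5 line for ALT or AST above 8 x ULN to match Table 4: interrupt at the first value, confirm by repeat test, contact the TA MD;
- insert the COVID-19 and ECG paragraphs in the French Section 6.1.7, and the thrombosis bullet in the French Section 5.4.1;
- use one perforation rule in both French sections;
- delete the methotrexate/placebo capsule and 14-week lines, which have no current effect because Period 1 is over.

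The cost is one local amendment, with ethics committee approval and regulatory approval where local law requires it (Section 9.1). It can go with the next amendment. No analysis has to be changed or rerun.
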